### **Case work**

Alongside all types of direct work outlined above, the therapists undertake case work. Case work includes communication with the client's social worker, and, where necessary:

- Writing solicitor support letters
- Legal advice
- Responding to age disputes
- Referrals into other services, such as mainstream mental health assessments, social activity, education, basic needs

### **Monthly clinical supervision**

Each therapist will have a minimum 1h per month of external 1-2-1 clinical supervision. This is defined by BACP's Ethical Framework:

*"A specialised form of mentoring provided for practitioners responsible for undertaking challenging work with people. Supervision is provided to ensure standards, enhance quality, advance learning, stimulate creativity, and support the sustainability and resilience of the work being undertaken."*

Supervision offers therapists a reflective space in which to develop practice and so benefits client safety. All aspects of a therapists' practice should be open to supervision.

### **Psychoeducational workshops (out of scope of the evaluation)**

These are one-off workshops offered to host organisations such as schools and colleges, receptions centres, existing youth groups etc. Workshops involve interactive activities to normalise mental health and symptoms, offer coping strategies, signpost for further help. They can also act as a referral route into My View.

Table 2: One to one and group therapy session structure

| Session s | Complete  | Content 1:1   | Content Group  |
|-----------|---|---|--|
| 1 - 3     | 
 
 Confidentiality mandate
 
 Risk Assessment
 
 Assess and prioritise needs together, including referrals
 
 YP CORE
 
 Identify goals
 
 | 
 
 Trust: Therapeutic Relationship – explain role of therapist and organisation
 
 Embodiment: Breathing techniques and grounding exercises
 
 Identity/role: Creative exercises (i.e. 5 things about me, personal flag etc.) – beginning to draw out secondary narratives beyond victimhood
 
  | 
 
 Trust: Therapeutic Relationship – explain role of therapist and organisation
 
 Embodiment: Breathing techniques and grounding exercises
 
 Identity/role: Creative exercises (i.e. 5 things about me, personal flag etc.) – beginning to draw out secondary narratives beyond victimhood
 
   |
| 4 -6      | 
 
 6 SESSION REVIEW – YP CORE, revisit goals
 
  | 
 
 Psycho-Education: normalising, normal response to abnormal events
 
 Psycho-Education: Extra offer of specific tools needed
 
 Bearing witness: Projection – explore support networks, story-making to assess coping mechanisms
 
 Creative exercises and/or talking about everyday experiences: exploration of alternatives (emotional responses, ways of communication, roles/identities etc)
 
 | 
 
 Psycho-Education: normalising, normal response to abnormal events
 
 Psycho-Education: Extra offer of specific tools needed
 
 Bearing witness*: Projection – explore support networks, story-making to assess coping mechanisms
 
 Creative exercises and/or talking about everyday experiences: exploration of alternatives (emotional responses, ways of communication, roles/identities etc)
 
 
*: by therapist and other group members
 |
| 7 - 9     | 
*Flag up ending in session 9
 
*explore and plan ending
   | 
 
 Bearing witness: projection - space to connect with past memories of identity and culture
 
 Bearing witness: narrative therapy exercises – reinforce secondary narratives of strength and coping ability – Tree of Life, Narratives in a Suitcase etc.
 
   | 
 
 Bearing witness*: projection - space to connect with past memories of identity and culture
 
 Bearing witness*: narrative therapy exercises – reinforce secondary narratives of strength and coping ability – Tree of Life, Narratives in a Suitcase etc.
 
  |

|         |  |   |   |
|---------|--|---|---|
|         |  | 
 
 Beginning to link creative explorations and/or change within the therapy space to everyday life; noticing changes, even small.
 
   | 
 
 Beginning to link creative explorations and/or change within the therapy space to everyday life; noticing changes, even small.
 
 
*: by therapist and other group members
   |
| 10 - 12 | 
Session 10 – review goals, consider onward referrals
 
Session 11 – YP CORE
 
Session 12 – what will you take away + what will you do this time next week
 | 
 
 Opportunity to reflect back and solidify any gains from therapy
 
 Opportunity to express and process emotions related to the upcoming (and past) endings
 
 Trust: Celebrate the therapeutic relationship and use it as a model for a new narrative about others and the world to possibly be established (if not here, then in 7-9 above)
 
 Embodiment: Use of rituals to mark and contain the experience of the ending
 
 Therapeutic relationship: invitation to internalise this and make it part of inner resources
 
 | 
 
 Opportunity to reflect back and solidify any gains from therapy
 
 Opportunity to express and process emotions related to the upcoming (and past) endings
 
 Trust: Celebrate the relationships in the space and use it as a model for a new narrative about others and the world to possibly be established (if not here, then in 7-9 above)
 
 Embodiment: Use of rituals to mark and contain the experience of the ending
 
 Therapeutic relationship: invitation to internalise this and make it part of inner resources
 
 |

## **A note on therapeutically trained translators**

The general expectation is that where possible, the same interpreter is used throughout the 12 sessions. Interpreters are mostly selected out of a pool of previously identified and trained interpreters. Refugee Council has a holistic approach to therapeutic work with refugees, which is underpinned by our commitment to linguistic justice and human rights. Interpreting is an integral part of services provided to clients with little or no English language and has the potential to enhance the therapeutic work and relationship. It is now widely accepted in the refugee therapy sector that whenever there is an interpreter present, there is a three-way relationship. The interpreter has a relationship with both the therapist and the client and cannot be made invisible or reduced to 'just a voice'.

Refugee Council's Good Practice Guidelines for Interpreters and Therapists Working Together underpins all work with refugees in therapeutic services across England and Wales. These guidelines apply to work with adults, children, young people, couples, families and in group contexts. The underlying principle that is the foundation of these guidelines is that interpreting is a skilled and complex endeavour and the interpreting team are integral to the therapeutic work with refugees.

Therapists and interpreters working in partnership should continue to develop anti-oppressive practices in their work, aiming to 'find unique and meaningful ways to hear the clients' voices that do not deny them power and replicate discriminatory experiences' (Bains, 2010: 23). The process of interpreting is naturally slower than direct one-to-one communication and this can mean that the practitioner has more time to reflect and prepare for their next intervention/interaction while the interpreter is translating. Refugee Council believes that it can be therapeutic for the client to be heard and understood by both the therapist and the interpreter.

The process of the translation allows the therapist more time to think and reflect on interventions, and it can help pace a session with a traumatised individual. When the therapist is from another culture, and their approach and demeanour is new or uncomfortable, the familiarity of the interpreter's language and presence can be containing and make therapy possible in the beginning. The gentle and warm presence of the interpreter can be felt as validating and reassuring to a client. When the trust in the therapist grows, the presence of two caring and supportive individuals being alongside an individual in pain can be affirming and therapeutically significant.

It is Refugee Council's commitment to offer a bi-monthly supervision group to interpreters who are regularly working within therapeutic services. A supervision group can be a helpful forum as it allows the facilitation of mutual support and learning between interpreters and creates a team that can support each other within their day to day work. It is useful for this to be facilitated by a therapist working within Refugee Council's therapeutic services.

## Short term outcomes

In the short term, i.e. at the end of 3 months after the intervention starts, it is hypothesised that the programme will improve young people's psychological and emotional wellbeing, as well as their emotional self-regulation and ability to cope. In addition, it is anticipated that the intervention will result in:

- Improved social connection and reduced social isolation
- Improved confidence / self-image
- Improved aspirations / view of future
- Improved physical wellbeing
- Improved safety / reduced risk of harm
- Increased willingness / openness to seek support / engage with other services
- Onward referrals to other services (made by BRC or Social Services).

The final two outcomes focus on the willingness of young people to engage with other services and whether referrals have been made but do not include actual access to other services. This is because the 3-month timeframe is often too short to see young people going on to access new services, which is linked to the length of time referrals can often take, for example, to CAMHS or to education i.e. a local college. Furthermore, while the British Refugee Council records onwards referrals to other services on their database, it is not possible to record whether or when this referral has been accepted or successful. Furthermore, the Refugee Council do not collect data about the referrals made by Social Services following the My View intervention, which are more common than referrals made by the Council.

It is also anticipated that the evaluation will improve the evidence base on what works for therapeutic interventions with UASC.

## Medium and long-term outcomes

In the medium and longer term, the intervention aims to achieve:

- Sustained improved wellbeing, which is anticipated to support the prevention of pathologies (i.e. clinical diagnoses) and improved home and school stability
- Successful onward referral to more intensive therapeutic intervention (which heavily depends on local waitlists)
- Successful onward referral to education (to the extent that there are local college places which can be accessed by clients)
- Improved social inclusion / integration.

Through the achievement of these outcomes, it is anticipated there will be cost savings for local authorities typically associated with, for example, placement or school changes and mental health and social care services.

# Impact Evaluation

## Research Questions

In line with the logic model, we hypothesise that children and young people who take part in the My View intervention will have better psychological and emotional wellbeing. Our impact evaluation research questions are:

- What is the effectiveness of the My View intervention for UASC in terms of their psychological distress (as measured by Young Person’s Clinical Outcomes in Routine Evaluation (YP-CORE) measure), compared to a waitlist comparison group?
- What is the effectiveness of the My View intervention for UASC in terms of their mental wellbeing (as measured by the SWEMWBS), compared to a waitlist comparison group?

These questions are relevant for children and young people participating in either one-to-one therapy (over 12 sessions) or group therapy, or a mix of both. The comparison group will include young people who will wait three months before receiving the intervention. During this time, they will not receive any intervention delivered by BRC. However, it is possible that these individuals may receive support from elsewhere, which may vary.

## Design

Table 3: RCT design details

|   |                                |  |
|---|--------------------------------|--|
| Trial type and number of arms            |                                | Non-blinded parallel two-armed randomised control trial with UASC individually randomised to a treatment or waitlist control group (on rolling basis)  |
| Unit of randomisation                    |                                | Young person   |
| Stratification variables (if applicable) |                                | Overall, 6 strata will be used, comprising of one high-risk stratum and five moderate risk strata defined by the British Refugee Council locations, which include four with physical geographical boundaries and a fifth with virtual boundaries. Allocation rates are 50 : 50 for UASCs in moderate risk strata and 66: 34 in high risk strata. |
| Primary outcome                          | Variable                       | Continuous variable – scores ranging from 0 to 40  |
|   | Measure (instrument, scale)    | Mean intervention group YP-CORE score compared to mean control group YP-CORE score collected at endline (3 months from start of intervention) by delivery staff i.e. therapists  |
| Secondary outcome(s)                     | Variable(s)                    | Continuous variable – scores ranging from 7 to 35  |
|   | Measure(s) (instrument, scale) | Mean intervention group SWEMWBS score compared to mean control group SWEMWBS score collected at endline (3 months from start of intervention) by delivery staff i.e. therapists  |

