## Outcome Measures

### Primary outcome measure

The primary outcome measurement is the Young Person's Clinical Outcomes in Routine Evaluation (YP-CORE) measure. The YP-CORE is a measure of psychological distress and is widely used in mental health and school counselling services. It is freely available to use.

The baseline YP-CORE measurement will take place at the pre-assessment session for young people randomised i.e. both the treatment and control groups. Data will then be collected at the following timepoints:

- Treatment group:
  - Baseline at the pre-assessment session
  - After six My View sessions (midpoint)
  - After three months of My View (endline / post-treatment)
- Waitlist control group:
  - Baseline at the pre-assessment session
  - After three months of being on the waitlist (endline) – this will be at a second pre-assessment session before the young person starts My View
  - After six My View sessions (standard practice, not included in the evaluation)
  - After three months of My View (standard practice, not included in the evaluation).

---

 We have used 47 cases per block as an approximation to the 280 total required (i.e.  $47 \times 6 = 282$ ).

 <https://www.ncbi.nlm.nih.gov/pmc/articles/PMC6860299/>

 <https://www.corc.uk.net/outcome-experience-measures/core-measurement-tools/>

 If, for any reason, the midpoint questionnaire (after 6 sessions) gets delayed and therefore becomes close to the endline questionnaire (to be completed after three months), therapists may decide to only collect the endline.

The measure is brief, with just 10 items covering anxiety, depression, trauma, physical problems, functioning and risk to self. As such, this covers the following short-term outcomes included in the programme's theory of change:

- Psychological and emotional well-being
- Emotional self-regulation
- Safety and risk of harm

For each item, the respondent selects one response to indicate how they have been feeling over the last week:

- Not at all
- Only occasionally
- Sometimes
- Often
- Most or all of the time

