## Missing Data

We anticipate that the baseline YP CORE questionnaire will be completed by all at the initial assessment interview, given the importance of the baseline in the analysis anyone not completing will be excluded from the analysis. Similarly, we anticipate the questionnaire measures of secondary outcomes to be collected at that same time. The endline primary outcome measures will be collected three months after starting the intervention with attempts

---

made to collect intermediate YP-CORE scores at the 6-week interval (for the treatment group only).

We anticipate that the key risks to missing data will arise with the endline outcome score. Cases without an endline score will not be imputed and will be dropped from the analysis, which will be run using complete case response data only. BRC routinely attempt to collect YP-CORE data after the first six weeks but only for the treatment group. Consequently, we cannot treat both groups equally with respect to missing endline data, so will not attempt to use the 6-weekly score for imputation purposes.

If there is evidence of differential attrition between the treatment and control groups in terms of socio-demographic characteristics, we will construct a weight to account for differential attrition and include a weighted version of the primary and secondary outcomes in the sensitivity analysis to check on the stability of the impact estimate.

If there is no evidence of differential attrition, no weighting will be undertaken.

It is possible, however considered highly unlikely, that young people may give partial responses to the baseline and/or outcome data and, if this occurs, item responses may be imputed to enable a more complete summary score.

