| Findings not applicable to future delivery in non-Covid-19 circumstances   | One basis of the evaluation is that there is value in exploring online delivery of services and that many services will continue online for young people who are remote / young people more confident with technology. Efforts will be made to distinguish features of programme delivery and implementation that might vary in non-Covid-19 circumstances.
Likelihood: Low/ Medium
Impact: Low / Medium  |

|  |  |
|--|--|
| Quality of the data collected by My View/British Refugee Council makes it difficult to detect impact | Therapeutic staff trained by My View programme managers. Importance of data collection re-iterated by workshop with evaluators. Baseline data to be scrutinised and additional training offered if necessary.
Likelihood: Low/Medium
Impact: High  |
| Young people drop out and no post-data can be collected  | Tracking of young person through referrer by therapist. Session 6 data collection to be used as fall-back.
Likelihood: Medium
Impact: High   |
| Difficulty collecting data from the control group  | Waitlist design means we can get accurate 'pre' recording. Monthly check-in by therapist or BRC admin with young people while on waitlist
Likelihood: Low / Medium
Impact: High  |
| Contamination / crossover between the treatment and control groups                                   | It is possible that young people assigned to the control group receive the treatment. This might be when a decision has been made to override randomisation in high-risk cases. It may also take place if, for example, a young person in the control group attends a drop-in group session (e.g. at the Kent Reception Centre). In both cases, this will be recorded so the evaluation will be aware of how often this happens, and if appropriate, undertake sensitivity analysis (e.g. conducting analysis with and without these individuals to detect any differential impact).
Likelihood: Medium
Impact: Medium |
| Timetable / delivery delays if therapists take longer than expected to recruit                       | Full complement of therapists currently recruited.
Likelihood: Low / Medium
Impact: Low / Medium   |

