### **Taking part in the intervention is voluntary**

We will collect data and report on whether young people attend the My View therapy sessions they are offered (as part of the intention-to-treat analysis). Young people have the option to decline the offer to take part in the intervention.

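### The primary endline is dated inconsistently and on different clocks by arm, and treatment-arm young people who decline therapy have no endline date

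*Protocol*

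**What the plan says.** The protocol dates the three-month measurement in several ways.

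- **Design, Table 3:** the primary measure is "Mean intervention group YP-CORE score compared to mean control group YP-CORE score collected at endline (3 months from start of intervention". The secondary outcome has the same timing. The Missing Data section repeats the start-of-intervention clock and has no separate wording for controls.
- **Primary outcome measure:** the treatment-arm endline is "After three months of My View (endline / post-treatment", and the control-arm endline is "After three months of being on the waitlist (endline", taken at a second pre-assessment session before therapy begins. Baseline is at the pre-assessment session in both arms.
- **Summary:** YP-CORE is measured at baseline and again 3 months later, with no distinction by arm.
- **Section on business-as-usual support for the waitlist group:** controls are offered My View three months after randomisation. The Randomisation section places randomisation before the initial assessment, and so before baseline.

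On non-participants, the protocol says that "Young people have the option to decline the offer to take part in the intervention". Primary Analysis makes intention to treat the main test and plans a treatment-on-the-treated estimate, on the assumption that scores can be obtained from non-compliers. Missing Data drops every case without an endline.

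On session-6 scores, the risk register (Table 7) answers dropout with "Session 6 data collection to be used as fall-back". Missing Data notes that only the treatment arm has an interim score, "so will not attempt to use the 6-weekly score for imputation purposes".

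**The concern.** A randomised comparison needs both arms measured at the same elapsed time from a common origin, and needs everyone randomised to have a measurement date. The protocol secures neither.

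No text sets a maximum gap between baseline and first session. Any such gap lengthens treatment-arm follow-up beyond three months from baseline. Controls measured at waitlist release, three months after randomisation, could have less than three months from baseline. Untreated change over that difference would enter the treatment coefficient.

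A treatment-arm young person who never starts has no date from which to count. The measure is also "collected at endline (3 months from start of intervention) by delivery staff i.e. therapists", and a decliner has no therapy sessions at which to be seen. If these young people go unmeasured and are then dropped, the exclusion follows from the endpoint definition and falls on one arm. The planned attrition weights are triggered by socio-demographic differences, so they need not detect or correct loss driven by declining therapy.

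If the session-6 line were followed, mid-therapy scores would stand in for endline scores in one arm only.

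**Working it through.** **1. The plan's own figure.** Inputs from the sample size section: two-sided alpha 0.05, power 0.8, R² = 0.5, 6 strata of 47 (N = 282), or 145:135 (N = 280).

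MDES = M × √[(1 − R²) / (P(1 − P)N)], with M = t(0.975, df) + t(0.80, df) and df = N − 2×6 − 1.

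- N = 282, P = 0.5: 2.812 × √(0.5 / 70.5) = 0.237.
- N = 280, P = 145/280: 2.812 × √(0.5 / 69.9) = 0.238.

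Both round to the stated 0.24. At the illustrative SD of 7.6 this is 0.24 × 7.6 = 1.82 points. The timing problem does not alter this figure.

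**2. The clocks side by side.**

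| Place | Treatment arm | Control arm |
|---|---|---|
| Table 3 | Start of intervention | Same wording; cannot apply |
| Missing Data | Start of intervention | Not stated |
| Primary outcome measure | Start of My View | Time on waitlist |
| Waitlist section | – | Release counted from randomisation |
| Summary | Baseline | Baseline |

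Randomisation comes first, then baseline, then first session. The clocks agree only if these three fall close together.

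**3. Unequal follow-up (illustration).** The documents give neither a start lag nor a rate of untreated change. Assume a lag of 2 to 8 weeks from baseline to first session and untreated drift of 0.25 to 1.0 points per month. Bias = drift × lag / (52/12).

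- Low: 0.25 × 2 / 4.33 = 0.12 points, 6% of 1.82.
- Middle: 0.5 × 4 / 4.33 = 0.46 points, 25%.
- High: 1.0 × 8 / 4.33 = 1.85 points, 101%.

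At zero lag it is nil. Its direction follows the drift.

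**4. Non-starters unmeasured (illustration).** Let a fraction f of the treatment arm never start, and let their mean endline differ from starters' by k. The whole-arm mean is the starters' mean plus f × k; the complete-case mean is the starters' mean. The shift is therefore f × k. With k = 0.5 SD (assumed):

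| f (assumed) | Shift (SD) | Share of 0.24 |
|---|---|---|
| 5% | 0.025 | 10% |
| 15% | 0.075 | 31% |
| 30% | 0.15 | 63% |

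This is before baseline adjustment. If the whole gap is already present at baseline, the plan's correlation of 0.71 leaves 0.5 × (1 − 0.71) = 0.145 SD. At f = 15% the shift is then 0.15 × 0.145 = 0.022 SD, about 9% of the MDES.

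**5. Precision.** If 5% to 30% of the 145 are lost this way, evaluable N falls to about 273 to 237, the MDES rises to 0.241 to 0.261, and power at 0.24 goes from 80% to 73%. Bias is the larger issue.

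**The case against.** The strongest reply is that this is loose wording rather than a biased design. The Summary gives a common clock, baseline is taken at the same session in both arms, and if therapy starts soon afterwards the clocks nearly coincide. That stands as a limit on size. No start lag is reported, and the activity-flow and CONSORT figures, which may bear on timing, could not be read in the copy available. It does not remove the contradiction in the definition of the primary endpoint.

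Four stronger readings are tempting, and the documents do not support them.

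- **That session-6 scores replace the endline in one arm.** Missing Data rejects this, for exactly the reason of asymmetry. The risk register line is a conflict to resolve, not an analysis rule. The ethics text says only that young people may feel worse before improving, so a direction of bias cannot be assumed.
- **That the treatment-on-the-treated and local average treatment effect estimates must fail.** Primary Analysis foresees collecting non-participants' scores, and the risk register foresees tracing through the referrer. What is missing is a date.
- **That the comparison becomes starters against all controls.** A control who does not want therapy may also miss the second pre-assessment session, so loss in that arm is possible too.
- **That "Session 11 – YP CORE" in Table 2 is a rival endpoint.** That table describes the therapy sessions, and the Activities section separately sets a three-month cut-off for the evaluation measure.

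**Conclusion.** The point holds as an inconsistency in the primary endpoint. Table 3 and Missing Data give a time point that controls cannot have. The outcome section uses a different origin in each arm, and neither origin is tied to the Summary's baseline or to the randomisation date that governs waitlist release. Treatment-arm decliners have no endline date under an intention-to-treat analysis that discards cases without an endline, which risks differential exclusion. The two session-6 statements contradict each other.

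The size and direction of any bias cannot be established from the documents. The illustrative shift from unmeasured non-starters, 31% of the MDES (10% to 63%), rests on an assumed non-start rate, an assumed 0.5 SD gap from starters, no endline for any of them and no baseline adjustment. It falls to about 9% in the central case if the gap already exists at baseline. Timing bias is small if therapy starts promptly. The defect is still worth correcting at any of these sizes, because scores not collected at the right time cannot be recovered later. No SAP was available, but the protocol itself fixes this time point, so the matter is not one left to a SAP.

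**What to change.** Define endline in both arms as 3 months from one common origin, with one stated window. Two origins fit the existing text.

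- **Randomisation** matches the waitlist section and gives everyone randomised a date.
- **Baseline assessment** matches the Summary. Because baseline follows randomisation, the control endline could then fall after the waitlist release point, so those passages would need reconciling.

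State that endline is collected from everyone randomised, whether or not therapy started, and how young people without therapy sessions will be reached. Align the Summary, Table 3, Primary outcome measure, Missing Data and the waitlist section. Delete the session-6 fall-back from the risk register so that it agrees with Missing Data.

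The cost is protocol wording, a date rule in the case database and some follow-up effort for decliners. The one small drawback is that late starters will have had fewer sessions by endline.

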## Summary

The My View therapeutic intervention for unaccompanied asylum seeking children (UASC) will be delivered by the British Refugee Council for 11 months between June 2021 and May 2022. It will be delivered by trained therapists in four physical (London, Kent, Birmingham, Leeds) locations and one therapist will operate remotely. In total, 280 UASC aged c. 12 to 18 at the start of the intervention will take part. My View contains either one to one therapeutic intervention over 12 one-hour long sessions (to be accessed by c. 190 young people), group therapy (to be accessed by c. 57 young people) or crisis intervention (to be accessed by c. 33 young people). The therapeutic interventions are supported by individual case work for each client, where relevant. For the purpose of the evaluation, the intervention period is 3 months.

The primary aim of the intervention is to improve the psychological and emotional wellbeing of UASC. The primary outcome measurement will be the YP-CORE, which will measure psychological distress at baseline and follow-up 3 months later. The secondary outcome measurement will be SWEMWBS, which will measure mental well being at the same time points as the YP-CORE.

The three elements of the evaluation are a randomised controlled trial, an implementation and process evaluation and a cost analysis. The evaluation will take place from June 2021 to June 2022.

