### **Young people in the control group (waitlist) will receive business as usual support**

Young people who are randomised to be on the waitlist will receive business as usual support. This support may vary depending on their location / local authority, the source of the referral and whether any other support can be provided. Due to the waitlist design, young people in the control group will be offered the intervention three months after the randomisation.

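### The primary endline is timed from different origins in different parts of the protocol and by arm, and a young person allocated to My View who never starts has no endline date

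*Protocol*

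**What the plan says.** The protocol times the same endpoint in five places.

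- **Summary:** YP-CORE is the measure "which will measure psychological distress at baseline and follow-up 3 months later", with no distinction by arm.
- **Design, Table 3:** both outcomes are "collected at endline (3 months from start of intervention) by delivery staff i.e. therapists", again for both arms.
- **Primary outcome measure:** the schedule is split by arm. Treatment is "After three months of My View (endline / post-treatment"; control is "After three months of being on the waitlist (endline", taken at a second pre-assessment session before My View begins. SWEMWBS follows the same time points.
- **Missing Data:** "The endline primary outcome measures will be collected three months after starting the intervention".
- **Ethics section on the waitlist group:** "young people in the control group will be offered the intervention three months after the randomisation".

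On the order of events, the Randomisation section places allocation before the initial assessment, and the baseline score comes after allocation: "The baseline YP-CORE measurement will take place at the pre-assessment session for young people randomised i.e. both the treatment and control groups".

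The Primary Analysis section commits to intention to treat. Its formula (2) needs outcome scores from non-compliers and assumes that they can be collected. The section on voluntary participation allows young people to decline My View. Missing Data drops anyone without an endline score, with no imputation.

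**The concern.** A two-arm comparison of endline scores needs both arms measured at the same distance from a common origin. If one arm's clock starts at therapy and the other's at joining a waitlist or at randomisation, any change in distress that would have occurred anyway enters the treatment coefficient.

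The second problem needs no assumption about timing. A young person allocated to My View who never attends has no start of intervention, so three months from that start is undefined. A control has a waitlist date whether or not therapy is later taken up. If staff follow the schedule as written, non-starters may never be given an endline date. They would then leave the analysis under the complete-case rule. That would be selective loss from a set that is meant to be intention to treat, and it would also remove scores that formula (2) relies on.

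**Working it through.** **1. The plan's own figure.** Inputs from the sample size section: 145 treatment, 135 control, R² = 0.5, two-sided alpha 0.05, power 0.8, 6 strata, and an illustrative SD of 7.6. For individual randomisation within fixed strata, with P the treatment proportion:

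MDES = (t₀.₉₇₅ + t₀.₈₀) × √[(1 − R²) / (P(1 − P)N)], with N − 13 degrees of freedom.

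- N = 282 (6 × 47), P = 0.5: 0.237.
- N = 280, P = 145/280: 0.238.

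Both round to the stated 0.24, and 0.24 × 7.6 = 1.8 points. The calculation contains no timing term, so the choice of clock does not change it.

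**2. Follow-up implied by each reading.** Let *a* be the time from randomisation to the baseline session, *b* the time from the baseline session to the first therapy session, and *c* any delay in the control's second pre-assessment session. The protocol gives none of the three. Months from baseline to endline:

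| Arm and reading | Interval |
|---|---|
| Treatment, start = first therapy session | 3 + *b* |
| Treatment, start = assessment session | 3 |
| Control, waitlist counted from baseline session | 3 + *c* |
| Control, waitlist counted from randomisation | 3 − *a* + *c* |

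Treatment minus control ranges over *b* − *c*, *a* + *b* − *c*, −*c* and *a* − *c*. With *c* = 0 the difference is never negative. It vanishes for any *a* and *b* only if the assessment counts as the start and the waitlist is also counted from the assessment. The protocol says neither.

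**3. Illustrative bias.** The standard error of the adjusted difference is

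7.6 × √[0.5 × (1/145 + 1/135)] = 0.643 points.

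With no true effect and a shift of *d* points, the two-sided rejection rate is P(|Z + *d*/0.643| > 1.96). The lag (net extra treatment follow-up) and the spontaneous change per month (taken as linear) are assumptions, not figures from the protocol.

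| Lag | Drift (points/month) | *d* (points) | Share of 1.8-point MDES | False-positive rate |
|---|---|---|---|---|
| 0 | any | 0 | 0% | 5% |
| 1 week | 0.25 | 0.06 | 3% | 5.1% |
| 2 weeks | 0.5 | 0.23 | 13% | 6.5% |
| 1 month | 0.25 | 0.25 | 14% | 7% |
| 1 month | 0.5 | 0.50 | 27% | 12% |
| 1 month | 1.0 | 1.00 | 55% | 34% |

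These rows take distress as falling over time, which favours My View. If distress rises, the same shift hides benefit.

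**4. Loss of non-starters.** The non-starter rate is also not given. If 10% of the treatment arm were dropped, power at 0.24 would fall from 0.81 to 0.79. At 30% it would be 0.73, with an MDES of 0.261. At modest rates the power cost is small, so the main harm is selection.

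**The case against.** The strongest reply is that no lag is stated, so none is shown. The list of procedures puts the initial assessment first among the intervention's own components, and Table 2 places YP-CORE, risk assessment and needs assessment in sessions 1 to 3. On that reading the intervention starts at the session where baseline is taken, and the treatment endline is baseline plus three months, as in the Summary. The waitlist statement in the ethics section dates an offer of therapy, not a measurement. The control endline depends on a second session that has to be booked and may run late or be missed.

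This stands, and it rules out three inferences that a reader might draw.

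- **That treatment follow-up is systematically longer.** It is the expected direction, but the size is unstated and *c* can offset it.
- **That only the treatment arm loses people.** A control who no longer wants My View can miss the second session. The protocol also plans tracking through the referrer and monthly waitlist check-ins.
- **That late treatment starters alone would overrun.** Randomisation runs to January 2022 and RCT data collection to April 2022, so a late control session could overrun as well.

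The reply does not remove the conflict. The schedule by arm describes even the controls' second pre-assessment as preceding the start of My View, which sits badly with counting the assessment as the start. The width of a visit window may be left to a SAP. The origin is already stated in the protocol, in ways that cannot all be followed, and therapists will collect scores on that basis.

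**Conclusion.** The point holds in a limited form. The protocol gives the primary endline conflicting origins, one of which controls cannot meet, and gives an allocated non-starter no endline date under an intention-to-treat analysis that drops missing endlines. Whenever therapy does not start at once, following the schedule by arm as written can be expected to measure the arms at different times since randomisation, unless a late control session happens to offset the lag.

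The size cannot be determined from the protocol. It runs from nothing at zero lag to 1.0 point at an assumed one-month lag and the highest assumed drift. The 34% rate belongs to that corner of the table and should not be read as the expected error rate. The direction depends on whether distress falls or rises without treatment. The non-starter gap depends on none of these assumptions, though how many scores it would cost is unknown. Scores taken at the wrong time, or never taken, cannot be recovered in the analysis, so the wording should be settled before collection begins.

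**What to change.** Reconcile the Summary, Table 3, the Primary outcome measure schedule, Missing Data and the waitlist paragraph to one origin for both arms and both outcomes. One candidate is three months after the baseline session, as the Summary already has it. Set one visit window that applies whether or not, and whenever, therapy starts, so that non-starters have a due date. Record the dates of randomisation, baseline, first session and endline for everyone, and report the baseline-to-endline interval by arm.

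If baseline is the origin, the control endline falls *a* later than three months from randomisation, the point at which the ethics section says controls are offered My View. The two statements must then be reconciled so that the control score still precedes therapy, as the schedule requires.

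The cost is protocol wording and a generated due date. The downside is that treatment-arm young people who start late will have had less therapy at endline, by the length of the lag; a one-month lag would be about a third of the three-month period. The sample size and the MDES of 0.24 do not change.
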